## 10. AUDIO RECORDINGS

There will not be any audio recording.

## 11. RISKS TO SUBJECTS

Psychological distress. The potential risks are negligible. There are no known risks associated with the procedures. Participants will be informed that they may feel slightly uncomfortable discussing some of their symptoms. Mild discomfort may be likely during the intervention session; however, this is unlikely to have a serious negative impact on the participant's wellbeing. Participants will be told they can withdraw from the study at any time. Participation or withdrawal from the study will not affect any benefits to which they are otherwise entitled. Special precaution will be taken to safeguard confidentiality. During assessments, if the study staff member is concerned about thoughts and planning of a suicide attempt, the study staff member will ask two follow-up questions: Do you have a desire to kill yourself that you think you might act on and Do you have a plan for killing yourself and intend to carry the plan out? With this information and available suicide assessment measures, the interviewer will evaluate the severity of the participant's suicide risk. If the participant is deemed to be at imminent risk, a safety plan will be initiated. All study staff will receive adequate training in suicidal ideation and risk assessment, and all work will be supervised by [name], who is a licensed clinical psychologist who is also employed at the VA Center of Excellence for Suicide Prevention, a national research, data, and education dissemination center for suicide prevention.

If the interviewer is concerned about imminent risk, we will use a procedure used in ongoing research studies: warm transfers to the National Suicide Prevention Hotline. Emergency procedures will be initiated if participants are determined to be at imminent risk for suicide using the risk assessment described above. Participants determined to be at risk will be asked if they are willing to be transferred to the National Suicide Prevention Hotline. Hotline responders are

Page 10 of 20

well trained in emergency procedures and have working protocols for locating callers and initiating rescues. Calls can be transferred with a four-step process.

It is possible that participants may refuse to be transferred to the Crisis Line or hang up. As a result, participants will be asked to use a landline so that the number can be tracked to an address if emergency services are needed. For participants who only have a cell phone, interviewers will begin each session by asking the participant for the address from which they are calling so that the clinician can send help if it is needed. Because participants may give a false address, clinicians will consult with Crisis Line responders who have a protocol for emergency responses for cell phone callers.

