# 6. INCLUSION AND EXCLUSION CRITERIA

Inclusion criteria: To be eligible, participants must be ages 18+, understand English, have internet access, screen positive for an active OUD on the OUD Module of the Structured Clinical Interview for DSM-5 Research Version (SCID-5-RV), and screen positive for loneliness by scoring at least a T-score > 60 on the NIH Toolbox Loneliness Scale.

Exclusion criteria: Consistent with previously used telehealth-delivered assessments, we will exclude any participant who does not understand consent. Potential participants who are in the process of detoxifying as measured by the Subjective Opiate Withdrawal Scale will also be excluded.

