## 9. STUDY PROCEDURES

Screening: The project coordinator will screen by phone following a script. Potential participants will provide verbal consent to complete the screening measures. Those individuals meeting eligibility who are interested in participating will be scheduled for a telehealth-based appointment to go over Consent, complete eConsent, and conduct a baseline assessment. Assessments and Intervention: Participants will be enrolled following consent and will complete the baseline assessment. Following the baseline assessment, participants will be randomized to condition (control or experimental) by a computer-generated algorithm. Participants will schedule a convenient time for their telehealth-based intervention sessions. Mid-treatment, posttreatment, and 30- and 60-day post-treatment follow-up assessments will also be conducted by telehealth. Participants will be paid \$40 each for the baseline and post-treatment assessment, \$20 for the mid-treatment assessment and \$30 each for the 30-day and 60-day follow-up assessments. Participants will also be paid \$20 for completing the first 3 sessions within 4 weeks. The posttreatment assessment will also include an exit interview for participants to describe acceptability of the intervention. All assessments and interventions will be conducted via Zoom (including toll-free phone option) or phone. If requested, participants will be sent a letter indicating study activities completed.

Randomization: We will randomize at the participant level using block randomization in groups of 4. All demographic and outcome variables will be assessed for baseline equivalency. Any between-group baseline differences will be controlled for statistically in all subsequent analyses with baseline differences being defined here as any absolute standardized mean difference (Cohen's d) greater than or equal to .15.

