## Warm Transfer Process

- 1. Press the **conference** button.
- 2. Dial [name] and a hotline responder will answer.
- 3. Describe the participants risk and provide name and telephone number.
- 4. Pressing the **conference** button and participants will be linked with hotline counselors.

Adverse Events (AE). AEs may include, but are not limited to: worsened physical or mental health, or inadvertent disclosure of confidential research information. Serious Adverse Events (SAE) may include: death, hospitalization due to worsening psychiatric symptoms or suicidal ideation, or all life threatening or disabling/incapacitating events among research participants. Per IRB regulations, SAEs, any event resulting in a deviation from the study protocol (e.g., emergency hospitalization to address suicidal behaviors) or death will be reported to the PI within 24 hours and to the IRB in 48 hours. This will be completed in order to assess significance and determine an appropriate response. AEs that involve temporary distress will be noted by interviewers and provided to the IRB in an annual report.

Confidentiality of Records. Numerous protections are in place to reduce the likelihood of loss of confidentiality. All research data will be kept in locked filing cabinets in secure areas, absent of identifying information, and coded by research number only. Files containing consent forms and other items with identifying information will also be kept in locked filing cabinets, but these will be separate from cabinets containing data from this study. All electronic data will be stored on a secure, password-protected server.

Should the individual elect not to participate in the study, they will be provided with a website containing available substance use and mental health treatment centers available across the country.

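### Section 11 asks for a current address only from participants without a landline, so a landline owner who joins Zoom by computer can be missed

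*Combined protocol and SAP*

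**What the plan says.** Section 9 (Study Procedures) sets the permitted modes of contact: "All assessments and interventions will be conducted via Zoom (including toll-free phone option) or phone". Section 6 requires that "participants must be ages 18+, understand English, have internet access" and does not list a telephone line among the criteria, although Section 9 has the coordinator screen candidates by telephone.

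Section 11 (Risks to Subjects) expects that some participants at risk will not accept transfer to the crisis line or will end the call. Its safeguard has three layers:

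- By default, "participants will be asked to use a landline so that the number can be tracked to an address if emergency services are needed".
- The exception is "For participants who only have a cell phone, interviewers will begin each session by asking the participant for the address from which they are calling". The stated purpose is to let the clinician send help.
- If the address given may be false, clinicians turn to "Crisis Line responders who have a protocol for emergency responses for cell phone callers". Section 11 also says that hotline responders have "working protocols for locating callers and initiating rescues".

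The Warm Transfer Process that follows is a conference-button sequence on a telephone. Section 11, as available, does not mention Zoom, video or a computer.

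**The concern.** The address question depends on which telephone a participant has, while the need for it depends on how the participant joins. The two agree as long as landline owners use their landline. They come apart when a landline owner joins Zoom from a computer. Section 9 permits that, and Section 11 does not deal with it.

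Recruitment is national and there is no in-person contact, so help can be sent only if staff know where the participant is at that moment. The protocol accepts this, since it asks participants who have only a cell phone for their address at each session. It also treats the population as one at raised risk: Section 2 links loneliness to suicidal behavior and names social isolation as a risk factor for it among people addicted to heroin. What is at stake is participant safety in a rare but serious event.

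**Working it through.** The plan gives no figure to reproduce, and no formula applies. The check is to run the rules of Section 11 through the modes of contact that Section 9 allows.

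1. **Landline owner, calling on the landline.** The number can be traced. Location is covered.
2. **Cell phone only, calling on it.** The address is asked at each session. Location is covered, with the responders' cell-phone protocol as back-up.
3. **Cell phone only, joining Zoom by computer.** The trigger is worded by what the participant has, not by how the participant joins, so the question still applies. Location is covered.
4. **Landline owner, joining Zoom by computer.** No landline call exists to trace. The participant does not have only a cell phone, so the question is not triggered. Location is not covered.

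The gap is case 4. Now suppose that a case 4 participant is judged to be at imminent risk, declines transfer and disconnects. What staff would have is:

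- **Stored identifiers.** The privacy and confidentiality section lists address and telephone number among them. The stored address is not described as the location during a session, and no step in Section 11 uses it.
- **A telephone number.** Staff can ring it, but someone who has just disconnected may not answer, or may not be near a landline.
- **Crisis-line back-up.** It is described for callers and cell phone callers, and in case 4 no call has been made.
- **Staff discretion.** The data and safety monitoring plan lets staff act at once to protect a participant. Discretion cannot recover a location that was never asked for.

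The question therefore has to come before the emergency, as it already does for participants with only a cell phone.

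**Size.** The number of contacts in case 4 is the number of all contacts, times the share held on Zoom by computer, times the share of those that involve a landline owner. The documents give neither share. Any count would only reflect the values assumed, so none is given. The documents also give no rate of imminent-risk events.

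**The case against.** The strongest reply is that the gap needs two things at once: a participant who has not followed the request to use a landline, and an interviewer who reads the trigger literally. Read by its purpose, the instruction would lead a sensible interviewer to ask anyone who is not on a traceable line. This stands in part and limits the weight of the point. It does not remove it. Participants are only asked to use a landline, Section 9 permits Zoom without conditions, and an emergency procedure should not depend on each interviewer inferring its purpose.

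Other safeguards also count: a safety plan at imminent risk, staff trained in risk assessment, and supervision by a licensed clinical psychologist. They bear on severity, but none of them supplies a current location.

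A reader might infer more than the text supports:

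- **That Zoom participants cannot be transferred to the hotline.** This does not follow. Candidates are screened by telephone and numbers are among the stored identifiers, so staff can ring the participant and then run the written steps. What is missing is a sentence of clarification.
- **That the hotline is left without a location because the third transfer step says "Describe the participants risk and provide name and telephone number".** This is weak. The sequence is offered to those willing to be transferred, and in its last step staff press the conference "button and participants will be linked with hotline counselors", so the participant can state a location. Refusal and disconnection are handled separately.
- **That no Zoom participant is asked for an address.** Case 3 shows otherwise.

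Finally, the appendices, the text between Sections 2 and 4, and the text at the end of Section 9 were not available. A telehealth start-up step could be written there.

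**Conclusion.** The point holds in a narrow form. In the available text, a landline owner who joins Zoom by computer has no line to trace and does not trigger the address question. Staff may therefore lack a current location if that person is at imminent risk and declines transfer or disconnects. This is a stated rule that fails in a mode of contact the protocol permits, so it is more than missing detail.

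The affected group is of unknown size and may be small. The finding rests on reading the trigger by telephone ownership, as it is worded, and on the unavailable text containing no other location check. It does not show that any participant would come to harm, and it has no bearing on the sample size, the analysis or the interpretation of the results. The change should be made because it is cheap and protects participants.

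**What to change.** **Main change, Section 11.** Replace the cell-phone condition with a rule for everyone: at the start of every assessment and intervention session, whatever the medium, staff ask for the participant's current physical location and confirm a call-back number. Both are stored with the identifiers, apart from the research data, as the privacy section already provides.

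**Clarification, Warm Transfer Process.** For Zoom contacts, staff keep Zoom open, ring the participant on the call-back number, and then run steps 1 to 4.

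**Cost.** Each participant has 6 sessions and 5 assessments (baseline, mid-treatment, post-treatment, 30-day and 60-day), so 11 contacts. With full retention that is 125 × 11 = 1,375 contacts. If the planned 20% attrition (25 participants) all came straight after baseline, it would be 100 × 11 + 25 × 1 = 1,125. At an assumed one minute each, staff time is 1,125/60 = 18.75 to 1,375/60 = 22.9 hours over the whole trial, less for participants who are already asked. A short amendment and one item in staff training are also needed.

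There may be a small loss of the anonymity that Section 9 (Measures) counts on for honest reports of opioid use. The extra address question falls only on those not already asked, and keeping the answer with the identifiers limits that loss.

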## Warm Transfer Process

- 1. Press the **conference** button.
- 2. Dial [name] and a hotline responder will answer.
- 3. Describe the participants risk and provide name and telephone number.
- 4. Pressing the **conference** button and participants will be linked with hotline counselors.

Adverse Events (AE). AEs may include, but are not limited to: worsened physical or mental health, or inadvertent disclosure of confidential research information. Serious Adverse Events (SAE) may include: death, hospitalization due to worsening psychiatric symptoms or suicidal ideation, or all life threatening or disabling/incapacitating events among research participants. Per IRB regulations, SAEs, any event resulting in a deviation from the study protocol (e.g., emergency hospitalization to address suicidal behaviors) or death will be reported to the PI within 24 hours and to the IRB in 48 hours. This will be completed in order to assess significance and determine an appropriate response. AEs that involve temporary distress will be noted by interviewers and provided to the IRB in an annual report.

Confidentiality of Records. Numerous protections are in place to reduce the likelihood of loss of confidentiality. All research data will be kept in locked filing cabinets in secure areas, absent of identifying information, and coded by research number only. Files containing consent forms and other items with identifying information will also be kept in locked filing cabinets, but these will be separate from cabinets containing data from this study. All electronic data will be stored on a secure, password-protected server.

Should the individual elect not to participate in the study, they will be provided with a website containing available substance use and mental health treatment centers available across the country.

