Social factors. Quality/Quantity of Social Interactions: The Duke Social Support Index-assesses several domains of perceived social support, including social network size, social interaction, social satisfaction, and instrumental social support. Research supports the psychometric properties of the DSSI scales. 77,78 Although all variables will be considered, analysis are focused on the role of the social interaction and social satisfactory scales as measures of quantity and quality of social interactions, respectively.

Table 1. Schedule and content of assessments

| Primary outcome                              |       |
|--|-------|
| Loneliness-NIH Toolbox Loneliness Scale      | S,B,F |
| Loneliness-UCLA Loneliness Scale             | B,I,F |
| Secondary outcome                            |       |
| Opioid use-TLFB                              | B,I,F |
| Mechanistic primary outcomes                 |       |
| Quality/quantity of social interactions-DSSI | B,I,F |
| Negative affect-depression, anxiety PROMIS   | B,I,F |
| Tertiary/exploratory outcomes/mechanisms     |       |
| Burdensomeness/belongingness-INQ-12          | B,F   |
| Craving - PCS                                | B,F   |
| OUD-SCID-5-RV opioid module                  | S,F   |
| Overdose risk behaviors-ORBQ                 | B,F   |
| Drug use consequences-InDUC-2R               | B,F   |
| Key descriptive variables                    |       |
| Possible SUD, substance use-ASSIST, TLFB*    | B,I,F |
| Physical functioning, sleep, pain-PROMIS     | B,F   |
| Profile-29                                   |       |
| Treatment utilization                        | B,F   |
| Demographics                                 | В     |
|  |       |

S-Screening; B-Baseline, I- Intervention; F-Follow-ups/Post; \*only TLFB for mid-intervention assessment

Belongingness: The Interpersonal Needs Questionnaire (INQ-12) assesses thwarted belongingness (i.e., an unmet need to belong) and perceived burdensomeness (i.e., feeling a burden to social support network). This measure will assist in identifying potential cognitive-related mediating pathway between loneliness and opioid use. Research supports the scale's psychometric properties.  We will also explore the quality and quantity of interactions via social media with friends, family, and strangers as there is a mixed results in this area. 

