Negative Affect. The depression and anxiety subscales from the PROMIS Profile-29 will be used to assess depression and anxiety. Research supports the psychometric properties of these scales.

Substance Use Disorder Screener. Lifetime and past three-month possible substance use disorder will be assessed using the NIDA-modified Alcohol, Smoking, and Substance Involvement Screening Test (ASSIST). The ASSIST is an 8-item screening measure originally developed by the World Health Organization to assess substance use and problems. The ASSIST asks about both "street" opioids and prescription opioids. Scores ranging from 0-3 suggest lower risk, 4-26 suggest moderate risk, and 27+ suggest high risk. The ASSIST has

Page 8 of 20

strong support for its reliability and validity. We will capture other substance use during the study period using the TLFB.

Physical health and overall functioning. The PROMIS Profile-29 will be used to assess the following domains: physical function, fatigue, sleep disturbance, ability to participate in social roles and activities, and pain interference, in addition to anxiety and depression domains noted above. There is strong support for the measure's psychometric properties.

Overdose Risk Behavior. The Overdose Risk Behavior Questionnaire (ORBQ) assesses the frequency of past-month engagement in behaviors that are associated with overdose. Higher scores on the ORBQ are associated with number of prior overdoses.

Treatment utilization. We will assess participant past and current utilization of pharmacological (e.g., buprenorphine, anti-depressants), psychological, and other supportive interventions (e.g., Narcotics anonymous, CBT) related to substance use and mental health at baseline and follow-up.

COVID questions. This questionnaire was developed to assess if a participant had been diagnosed with the COVID-19, how the disease affected them, if they knew anyone who was diagnoses with COVID-19, and the extent to which the pandemic has affected them across a variety of domains in the last year.

Demographics. At screening, we will assess participants' gender, age, educational background, employment, income, race, ethnicity, marital status, and cohabitation status.

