# 16. DATA AND SAFETY MONITORING PLAN

Data Safety. To ensure safety of participants in the study proposed and validity and integrity of data collected, the PI ([name]) will oversee all data and safety monitoring functions and the research team will be advised that he will be the primary contact overseeing these activities. The PI and the research team will meet regularly to monitor study progress and discuss the implementation of monitoring procedures. He will also meet regularly with the research coordinator and to review monitoring procedures and ensure all efforts are being taken to minimize risks to participants. The PI will have an independent Data Safety Monitoring Officer (DSMO) to help monitor safety issues. The DSMO will be at least an Assistant Professor at University of Rochester who is independent of this study and has substantial randomized clinical trial experience for individuals with substance use disorder or mental health condition. As indicated below, the PI will track all negative outcomes and incidents as well as conduct interim data analysis every 12 months after the study has started. The study design will be significantly modified (and even screening stopped) on the suggestion of the DSMO that the study is creating potential harm to our participants.

The PI will regularly oversee all aspects of the study, including participant recruitment, informed consent, data collection, management, and analysis, as well as regularly assess the risk/benefit ratio associated with participation in the study. All research staff will participate in an intensive training to help them understand the importance of reducing the risk for participants and learning how to recognize and report any AE or SAE. SAEs may include: death, hospitalization due to worsening psychiatric symptoms or suicidal ideation, or all life threatening or disabling/incapacitating events among research participants. AEs may include, but are not limited to: physical injuries, worsened physical or mental health, or inadvertent disclosure of confidential research information.

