If an SAE occurs, the PI will immediately contact the DSMO and IRB, followed by a written report in 24 hours. He will make a decision whether there is sufficient evidence to suspend data collection, allow for further IRB review, modify the protocol, or make other changes to reduce potential risk to participants. The study will resume based on agreement of the PI, an IRB member, and the DSMO. In the event that an AE that is not an SAE is reported to the PI, the PI will discuss the event with the DSMO. Immediate evaluation will occur to determine if any extra steps can be taken to minimize the likelihood of that type of AE occurring again. If changes can be made, a report/amendment will be written and submitted to the DSMO and IRB.

Page 13 of 20

As part of a standard practice, the PI will supervise the implementation of one audit within 4 months after study recruitment with subsequent audits each year of the materials collected and produced as part of the study to ensure proper confidentiality and compliance with ethical principles, including informed consents, electronic medical record documentation, questionnaire data, and to make sure that the research staff are following established protocols. The PI will provide an annual summary report of all AEs to the IRB and the DSMO as part of the annual review. If no adverse events have occurred, the report will state, "No adverse events affecting human participants have occurred during this project year."

Data Monitoring. To ensure adequate participant recruitment and enrollment, each week, the PI will discuss the current number of participants contacted, screened, and enrolled from each site and compare those numbers to the expected based on our preliminary data. If after the first 4 months, it appears we are not reaching our expected number of participants, the PI will discuss potential barriers/obstacles and solutions with the DSMO. Discussions regarding recruitment and enrollment will continue at each meeting with the DSMO to ensure proper implementation of the study.

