include all data up to and including 2 weeks prior to the reporting deadline (except for SAEs, which are to be reported within 24 hours of an event). For each meeting at which the study is to be considered or monitored, the PI will present an overall progress statement containing the assurance that the PI has considered the clinical trial's progress and that there is/is not evidence of safety issues that should be addressed by the DSMO. The reports will also include information related to problems in recruitment, biases in attrition, biases with respect to AEs, or other operational problems that affect the integrity of the study. At the additional request of the DSMO, interim analyses will be conducted to determine whether the emerging findings may lead to a discussion of discontinuing the trial early.

The DSMO will be kept apprised of all SAEs and AEs on an ongoing basis and will decide whether individual patients should be removed from the protocol. Although research staff, under the PI's supervision, are able to take whatever immediate action is necessary to safeguard the welfare of individual patients, the DSMO will be called on whenever possible to make decisions as a result of a SAE. There may be rare instances where some unanticipated situations occur that may affect participant welfare. In these situations, the IRB or the DSMO may be contacted to help resolve the situation.

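### The visible plan schedules no adverse-event or overdose question, and its serious-event lists name hospitalisation only for psychiatric causes, so non-fatal overdoses and medical admissions are likely to be under-recorded

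*Combined protocol and SAP*

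**What the plan says.** **How events come to light.** In section 11 (Risks to Subjects), the adverse-event paragraph after the warm-transfer steps says "AEs that involve temporary distress will be noted by interviewers and provided to the IRB in an annual report". Earlier in that section, two suicide follow-up questions are put only if a staff member is already concerned. In the Data and Safety Monitoring Plan, staff are trained to recognise and report events, the PI tracks negative outcomes, and a non-serious event goes to the monitoring officer (DSMO) once it has been reported to the PI.

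**Definitions.** Section 11 has "AEs may include, but are not limited to: worsened physical or mental health, or inadvertent disclosure of confidential research information" and "Serious Adverse Events (SAE) may include: death, hospitalization due to worsening psychiatric symptoms or suicidal ideation, or all life threatening or disabling/incapacitating events". The monitoring plan repeats the serious list, including "hospitalization due to worsening psychiatric symptoms or suicidal ideation", and adds physical injuries to the non-serious list. Neither section names overdose.

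**Measures.** Table 1 lists "Overdose risk behaviors-ORBQ" at baseline and at post-treatment and follow-up. The text says that this instrument "assesses the frequency of past-month engagement in behaviors that are associated with overdose". Treatment utilization is restricted to care for substance use and mental health.

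**Use of the data.** PI reports to the DSMO are to cover "biases in attrition, biases with respect to AEs". If nothing has been recorded, the annual summary is to read "No adverse events affecting human participants have occurred during this project year".

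**The concern.** Spontaneous reporting finds what participants choose to mention or staff happen to notice. Every contact here is by video or phone, and active opioid use disorder is required for entry. A non-fatal overdose or a medical admission between contacts leaves no trace unless someone asks. Overdose death is also the first fact in the protocol's rationale.

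Two things are at stake. The DSMO can prompt modification of the trial for harm, and would be working from counts of unknown completeness. And the annual statement that no events occurred would look like a finding when it might only reflect that nobody asked.

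**Working it through.** The plan states no adverse-event rate, safety comparison or safety sample size, so there is no figure to reproduce. The check is mainly of text against text.

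**Step 1. Does any described measure ask about the event itself?**

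| Instrument | What it is described as recording | Overdose event or medical admission? |
|---|---|---|
| Timeline Follow Back | Days of opioid and other substance use | Not described |
| ORBQ | Past-month overdose risk behaviours | Behaviours, not events |
| InDUC-2 | Consequences in five domains, one physical, since the previous assessment | Not described |
| Treatment utilization | Care for substance use and mental health | General medical admissions not named |
| PROMIS Profile-29 | Symptom and function scores | No |
| SCID-5-RV opioid module | Diagnosis at screening and final follow-up | No |
| COVID questions | COVID-19 diagnosis and effects | Not described |

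Table 1 is not exhaustive: the emotion-invalidation and attachment scales, for example, are missing from it. The narrative descriptions were therefore checked as well, and they add no safety enquiry.

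**Step 2. Where do the definitions leave a gap?**

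| Event | In the serious list? | Remaining gap |
|---|---|---|
| Death | Named | Detection only |
| Overdose or medical event that is life-threatening or disabling | Covered, any cause | Detection only |
| Admission for psychiatric worsening or suicidal ideation | Named | Detection only |
| Other medical admission | Not named; can count as worsened physical health | Detection and classification |
| Overdose not judged life-threatening | Not named; can count as worsened physical health | Detection and classification |

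Classification matters because serious events go to the IRB and DSMO on an expedited route, while others wait for discussion or the annual report.

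**Step 3. Could recording differ by arm?** Both arms have six sessions of about 45 minutes. CBT-L takes a case history and works through distress and drug-related beliefs; the control covers diet, water, exercise and sleep. Therapists necessarily know which they are delivering. With equal true risk p in both arms and capture probabilities c₁ (CBT-L) and c₀ (control), expected recorded events are 63·p·c₁ and 62·p·c₀. The ratio of recorded risks is then c₁/c₀. It is 1 if capture is equal, above 1 if CBT-L invites more disclosure, and below 1 if the control's physical-health topics bring out more medical events. The documents give neither c₁ nor c₀.

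**Step 4. What would a report of no events mean?** Suppose all 125 participants contribute independently and none has a recorded event. The one-sided 95% upper limit for the probability of a recorded event is 1 − 0.05^(1/125) = 0.0237, or 2.4%. The limit for the true risk is that figure divided by the capture probability c:

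- c = 1.0: 2.4%
- c = 0.8 (assumed): 0.0237/0.8 = 3.0%
- c = 0.4 (assumed): 0.0237/0.4 = 5.9%

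The values of c are illustrative. With c unknown, as under spontaneous reporting, no limit on the true risk can be quoted.

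**The case against.** The strongest reply is that the plan is less bare than a quick reading suggests, and several stronger readings fail.

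- **That only psychiatric admissions can be serious.** A reader might infer this. The lists say what events may include, and they cover every life-threatening or disabling event whatever its cause. A lesser medical admission still fits the non-serious definition, and once reported it reaches the DSMO. The risk for that group is non-detection or misclassification, not exclusion by definition.
- **That all adverse events are recorded only when volunteered.** The sentence about interviewers covers temporary distress alone. Staff training and PI tracking also exist. They deal with recognising and logging an event, however, and no available text says how one is found.
- **That counts by arm are skewed towards CBT-L.** The documents do not show this. The assessment schedule is the same in both arms, the assessing coordinator is blinded, and contact time is matched. The direction could run either way, and section 17 plans no comparison of adverse events by arm. What stands is that blinded assessments protect the comparison only if harms are asked about there.
- **That the ORBQ's one-month window leaves early treatment unobserved.** The Timeline Follow Back is completed at every assessment, including mid-treatment, and the InDUC-2 looks back to the previous assessment. Substance use and its consequences are therefore followed through that period, although neither instrument is described as recording overdose events or admissions.
- **That the point is minor.** The protocol calls the risks of a psychosocial intervention negligible. That bears on expected causation. It does not make it unnecessary to know which events occur in a high-risk population.

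Finally, the text between sections 2 and 4, and between the measures and section 10, was not available. Section 11 mentions suicide assessment measures that the visible list does not identify, so relevant material may lie there.

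**Conclusion.** The point holds in limited form. On the visible text there is no systematic enquiry about adverse events or overdoses, and the serious-event lists do not name non-psychiatric admission or non-fatal overdose. Under-recording is likely. The definitional gap is confined to medical admissions and overdoses that are not life-threatening or disabling; for the severe ones the gap is in finding them. Recording that differs by arm is possible, but it cannot be quantified or given a direction from the documents. A statement that no events occurred would be uninterpretable.

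The conclusion assumes that the unavailable pages contain no adverse-event form or overdose question. If they do, the detection part falls and only the wording of the definitions remains. This should be fixed, but it does not undermine the efficacy analysis.

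**What to change.** 1. Add one row to Table 1: a short fixed safety checklist, asked of every participant by the blinded coordinator at the mid-treatment, post-treatment, 30-day and 60-day assessments. It should cover the time since the last completed assessment, so that a missed visit leaves no hole. Items: overdose; emergency visit or hospital admission for any cause; suicidal behaviour; other worsening of physical or mental health.
2. Base any summary of adverse events by arm for the DSMO on these solicited answers, and list therapist-reported events separately.
3. In section 11 and in the Data and Safety Monitoring Plan, name hospitalisation for any cause and non-fatal overdose in the reporting definitions, with the same wording in both places.
4. Word the annual statement so that it says how events were sought and how many participants were asked.

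The cost is a few minutes at visits already scheduled and the wording of an amendment. The downside is more events to record and report, many of them unrelated to the intervention.
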